Symptom questionnaires will be collected at an enrollment visit (V1), and participants will be randomly assigned to the EI or DI groups. For those in the EI group, the intervention will begin 0-7 days thereafter. Sessions will be administered over 10 business days. Follow-up data collections will be obtained at 2 weeks following enrollment (V2) [0-14 days after completion of the intervention for the early intervention group], and 4-7 weeks after the V2 (V3, primary outcome). Following V3, those in the DI group will be offered the opportunity to cross over to receive 4 CR intervention sessions and will continue to be followed for data collections at 0-14 days (V4) after completing their sessions, and 4-7 weeks (V5) after V4. Mean contrasts will be used to compare the changes in measures of perceived stress (PSS) from V1 to V3, the primary outcome, in the early vs. delayed intervention groups. Similar analysis will occur for secondary outcomes.

Background, Rationale, and Context:

Background:

Abnormal electroencephalographic (EEG) asymmetries have been reported in a variety of neurological, cardiovascular, and psychophysiological conditions including insomnia, attention deficit hyperactivity disorder (ADHD), anxiety, autism spectrum disorders, depression, dyslexia, post-traumatic stress disorder (PTSD), and traumatic brain injury (TBI) (Avram, Baltes, Miclea, & Miu, 2010; T. S. Hale et al., 2010; Hale et al., 2009; T.S. Hale et al., 2010; Kemp et al., 2010; Lazarev, Pontes, Mitrofanov, & deAzevedo, 2010; Marzano, Ferrara, Sforza, & De, 2008; Metzger et al., 2004; Moscovitch et al., 2011; Rabe, Beauducel, Zollner, Maercker, & Karl, 2006; Riemann et al., 2010; Spironelli, Penolazzi, & Angrilli, 2008; Stroganova et al., 2007; Thibodeau, Jorgensen, & Kim, 2006; Wolynczyk-Gmaj & Szelenberger, 2011). Many, if not all of these conditions are associated with autonomic imbalance and

psychophysiological dysfunction manifested as low heart rate variability or other abnormal measures (Beckham et al., 2003; H. Cohen et al., 2000; Katz-Leurer, Rotem, Keren, & Meyer, 2010; Spiegelhalder et al., 2011; Tobaldini et al., 2013).

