*** = P < 0.001								

 Table 1. Preliminary Data: Cereset Outcomes from Exploratory Open-label Study

Version 1.1 08.02.2022 Note: The mean (SD) duration from last session to V2 was 3.9 (6.0) days, from last session to V3 was 42.7 (8.6) days, last session to V4 was 83.4 (12.4) days for the table above.

Cohorts within this exploratory study are published for pain and caregivers. (C. Tegeler et al., 2021a, 2021b)

This pilot study will evaluate the effects of using this more standardized, approach, and fewer sessions with CR, in participants with self-reported symptoms of stress.

Importance:

This randomized, waitlist-controlled study will evaluate the effects of the use of CR intervention in healthcare workers with symptoms of stress during the period of COVID-19. Healthcare workers of all types have been impacted personally, professionally, and financially by the pandemic, resulting in higher levels of stress and anxiety. Additional, brief, noninvasive, non-drug strategies are needed to help mitigate the effects of the acute trauma associated with the pandemic. The primary outcome will be change in Perceived Stress Scale (PSS) a measurement of how different situations affect feelings and perceived stress, in the early intervention group compared to delayed intervention control. Data will also be collected on a variety of additional relevant symptoms including insomnia, anxiety and autonomic cardiovascular regulation, for which benefits have been shown in prior studies using HIRREM. Data collected will assess the effects of a low dose CR approach (only 4 sessions) to help participants begin to mitigate stress. A successful outcome of reduced stress would suggest benefit for this more scalable, generalizable approach to the use of the CR technology. The effect of this minimalist approach on autonomic function and other self-reported symptoms will also be explored. This information will be useful for planning larger randomized trials in more homogeneous cohorts and evaluating the appropriateness of direct clinical implementation of the intervention. The proposed study might also help to identify characteristics of individuals who may experience differential effects/benefits from this low dose application of CR.

Healthcare Worker Burden:

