Event	Enrollment (V1) Baseline Data Collection	Baseline Recording and Session 1 (E1) { Within 0-7 days of V1 }	Session 2 (E2)	Session 3 (E3)	Session 4 (E4)	Post Intevention (V2) Data Collection {Within 0-14 days of E4/10-21 days post enrollment}	Post Intervention (V3) Data Collection {Within 4-7 weeks of V2}	Crossover Baseline Recording and Session 1 (D1) {Within 3 months of V3}	Crossover Session 2 (D2)	Crossover Session 3 (D3)	Crossover Session 4 (D4)	Post Intervention (V4) Data Collection {Within 0-14 days of final D4 Intervention}	Post Intervention (V5) Data Collection {Within 4-7 weeks of (V4) data collection}
Informed consent	х												
Demographics	х												
Perceived Stress Scale (PSS) - Standard	х						x						х
Perceived Stress Scale (PSS) - Since last data collection						x						x	
Insomnia Severity Index (ISI) - Standard	х						x						х
Insomnia Severity Index (ISI) - Since Since last data collection						x						X	
Center for Epidemiological Studies Depression Scale (CES-D)						x	x					x	х
Generalized Anxiety Disorder 7-Item (GAD-7) - Standard							x						х
Generalized Anxiety Disorder 7-Item (GAD-7) - Since last data collection						x						x	
PTSD Checklist for Civilians (PCL-C) - Standard	х						x						х
PTSD Checklist for Civilians (PCL-C) - Since Since last data collection						х						x	
Fatigue Severity Scale (FSS)	x					х	x					х	х
Quality of Life Scale (QOLS)	х					х	x					х	х
Interpersonal Support Evaluation List (ISEL-12)	х					x	x					х	х
Multiple Ability Self-Report Questionnaire (MASQ)	х					x	x					х	х
Depression, Anxiety, and Stress Scale (DASS-21)	х					x	x					х	х
EQ-5D Self-Report Health State Question	х					x	x					х	х
WHO's Heath and Work Performance Questionnaire (HPQ)	х						x						х
Healthcare Utilization	х						x						х
COVID Questions	х					x	x					x	x
COVID Healthcare Worker Study Barriers to Participation Survey							x						х
FAROS HRV Recording	x					x	x					x	х
Randomized {EI=Early Intervention DI=Delayed Intervention }	х												
Cereset Research Intervention		X	Х	х	Х			Х	х	х	х		
Study Coordinator Data Entry	х					х	x					x	х
Technologist Data Entry		X	X	X	Х			Х	X	х	Х		

Cereset Research – COVID-19 Study Flow Chart:

Crossover DI Group

Crossover:		V4 Within 0-14 days of final		V5 Within 4-7 weeks of V4
-Short baseline recording		intervention session (up to 45 minutes)		(up to 45 minutes)

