-4 sessions over 10 calendar days (60 minutes each)	\rightarrow	-Repeat outcome measures	\mapsto	-Repeat outcome measures
				-Study completed for DI group

Enrollment Visit:

Informed consent is obtained, medical history and medication list are reviewed from the screening form (Appendix C), and collection of baseline measures is completed. This will occur prior to the start of CR and will require about 45-60 minutes of time. To promote good mental health and well-being, all participants will receive a listing of behavioral health resources at the V1 study visit.

Number of CR Sessions and Length of Study:

All baseline measures will have been collected during the enrollment visit. Participants in the IE group will begin CR sessions 0-7 days following V1 data collection, and will receive 4 CR sessions, along with continued care. CR sessions will occur while relaxing in a zero gravity chair, and are approximately 1 hour in length. The first two sessions must be received over 5 calendar days and all four should be completed within 10 business days.

Participants in the IE group who begin sessions immediately after V1, receive sessions, have V2 immediately, V3 four weeks after, may be in the study about 5 weeks. At the other end of the spectrum, a participant who delays the start of sessions until 7 days after V1, and receives sessions, then does not get V2, or V3 until the end of the allowable visit windows, might be in the study for about 8-9 weeks. The DI group may be in the study for 10 to 18 weeks.

Post-Intervention Data Collection Visits:

Within 7 days after completion of the intervention, participants in the IE group will return for a postintervention data collection visit (V2). Measures will be repeated. This visit will take about 30-45 minutes. Those in the DI group will return for V2 10-21 days after V1, with target of 14 days.

Between 4-7 weeks after completion of the V2, participants will return for the primary outcome data collection visit (V3). This visit will require about 30-45 minutes, and will be considered the time point for assessing primary outcomes. At the V3 visit, those in the EI group will be done with the study. Those in the DI group will be offered the opportunity to crossover and receive sessions within the next month. After receiving sessions, there will be V4 and V5 data collections.

Brainwave Assessment:

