The short baseline brainwave recording occurs as part of the first session. The assessment creates a map of frequencies and amplitudes. Our pilot data also suggest that this information is also useful for correlating with autonomic function (HRV), and that changes can be observed in frequencies and amplitudes from pre- to post-intervention. For the assessment, with the participant in a sitting position, sensors are sequentially placed over up to two areas of the scalp to record two-minute epochs of data while the brain is at rest with eyes closed. For the assessment, measurements are taken at homologous regions of the bilateral hemispheres according to the 10-20 International System at FP1/FP2 and T3/T4, and F3/F4 and P3/P4. The data are processed to identify patterns and imbalances of frequencies and amplitudes. The baseline brainwave assessment takes about 5 minutes to complete.

CR Sessions:

Each session requires about 1 hour, and will include 2 paired protocols, working with different locations on the scalp. Each protocol will typically last between 8-12 minutes. For the sessions, with the subject comfortably at rest, sitting or reclining in a zero gravity chair, the sensors are placed over the specific target areas on the scalp corresponding with brain regions/lobes to be observed. Frequencies and amplitudes are monitored in real time, and the dominant frequency within a chosen target frequency band, e.g. delta (0.5-3 Hz) is identified. The dominant frequency is assigned an auditory tone, which is played back to the subject via earbuds with as little as a 4-8 millisecond second delay. Thus, the brain pattern is echoed back to the participant from moment to moment, providing the brain with rapid updating about its frequencies, amplitudes, and patterns. All protocols will occur with eyes closed, and participants will be instructed to relax. Participants can fall asleep if they wish, without loss of effect since no conscious, cognitive activity is required with this closed-loop approach.

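### V2 heart rate and HRV may be recorded on the day of the last session in the early arm only, so exploratory V2 comparisons can mix acute post-session state with treatment effect

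*Combined protocol and SAP*

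**What the plan says.** All references are to the combined protocol and SAP.

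- **V2 timing, early arm.** The Abstract places V2 "0-14 days after completion of the intervention for the early intervention group". The Schedule of Activities column heading gives "Within 0-14 days of E4/10-21 days post enrollment". Number of CR Sessions and Length of Study describes the shortest course: "Participants in the IE group who begin sessions immediately after V1, receive sessions, have V2 immediately" (IE is the plan's variant of EI). Post-Intervention Data Collection Visits instead limits V2 to 7 days after the intervention and gives no lower limit.
- **V2 timing, control arm.** "Those in the DI group will return for V2 10-21 days after V1, with target of 14 days". Controls continue their existing care alone until V3.
- **V4 timing.** The Schedule of Activities allows 0-14 days after the last crossover session.
- **The session.** It lasts about 1 hour in a zero gravity chair. Protocols run with eyes closed and participants are told to relax. CR Sessions adds: "Participants can fall asleep if they wish, without loss of effect".
- **The recording.** The Faros row is marked at V1 to V5. The HR and HRV section specifies 10 minutes seated with normal breathing and analyses the first 5 usable minutes.
- **Status and analysis.** HR and HRV are exploratory. The Analytical Plan describes mean contrasts from V1 to V3 for PSS and extends the approach to secondary and exploratory outcomes. Mixed models are optional.

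**The concern.** Heart rate and HRV are momentary measures, so the circumstances just before a recording belong to what is measured. The V1 recording is taken before CR starts, and the control arm's V2 recording cannot follow a session. The early arm's V2 recording can. Randomisation does not balance this difference, because it comes from the assigned arm.

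If V2 HRV improves in the early arm, two explanations then compete: a change in autonomic regulation after four sessions, or the passing state of someone who has just spent about an hour at rest. The plan offers autonomic regulation as a possible route of benefit, and HR/HRV is the only physiological outcome scheduled at the data collection visits of an open-label trial that otherwise rests mainly on self-report. A V2 result may therefore be given weight. At V4 there is no concurrent control, so the same difficulty appears there as a within-person comparison of recordings made under different conditions.

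**Working it through.** No figure in the plan needs reproducing for this point. The check sets the timing rules side by side and then asks what the one available number can say.

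**1. Is day 0 allowed?** The Abstract and the Schedule both start the early arm's window at 0 days. The visit section sets an upper limit of 7 days and no lower one. The 7-day and 14-day upper limits conflict, but both admit day 0.

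**2. Does the 10-21 day limit exclude it?** The visit section attaches that limit to the control arm. The length-of-study section agrees: a shortest stay of about 5 weeks with V3 four weeks after V2 puts V2 at about 5 − 4 = 1 week after V1, before day 10. Even if the limit applied to both arms, sessions may start up to 7 days after V1 and run over 10 business days, so session 4 can fall on day 10 or later.

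**3. Is there a safeguard elsewhere?** The HR and HRV section sets no minimum time since a session, no rest period common to both arms and no order relative to a session. The Analytical Plan neither adjusts for nor examines this interval.

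**4. What precedes a same-day recording?** A session of about 1 hour contains 2 paired protocols of 8-12 minutes each:
- each pair counted once: 2 × 8 = 16 to 2 × 12 = 24 minutes with eyes closed;
- each pair counted as two protocols: 4 × 8 = 32 to 4 × 12 = 48 minutes.

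So eyes-closed protocol time is about 16-48 minutes within about an hour of relaxed rest.

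**5. How often?** The documents do not say. The nearest figure is the note to Table 1 on the exploratory study: "The mean (SD) duration from last session to V2 was 3.9 (6.0) days". The coefficient of variation is 6.0/3.9 = 1.54, which indicates right skew for a quantity that cannot be negative. It does not fix the share at day 0, as two simple distributions show:
- No same-day visits: 81% at day 1 and 19% at day 16.3. Mean = 0.81 × 1 + 0.19 × 16.3 = 3.9; SD = 15.3 × √(0.81 × 0.19) = 6.0.
- Many same-day visits: a share p at day 0 and the rest at day x. Then p/(1 − p) = 6.0²/3.9² = 2.37, so p = 0.70 and x = 3.9/0.30 = about 13. Mean 3.9, SD 6.0.

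The figure is compatible with none and with about 70%.

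**6. How much could it move V2?** If a share f of early-arm recordings carry an acute shift of a SD units, the V2 contrast moves by f × a. Neither value is in the documents. As an assumption only, f = 0.25 to 0.50 and a = 0.2 to 0.6 give 0.25 × 0.2 = 0.05 SD to 0.50 × 0.6 = 0.30 SD. With 69 per arm (138/2, assuming equal allocation), the chance of a significant result in the direction of the shift, with no lasting effect, is Φ(f × a × √(69/2) − 1.96):
- 0.05 SD: Φ(0.29 − 1.96) = about 5%;
- 0.30 SD: Φ(1.76 − 1.96) = about 42%.

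Without any shift it is 2.5%. The 42% is the extreme corner of the assumed range.

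**7. What is not touched?** V3 falls 4-7 weeks after V2, and controls cross over only after V3. Neither arm has a session shortly before the V3 recording.

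**The case against.** The strongest reply is that little planned inference is exposed. The Analytical Plan names V1 to V3 as the contrast, and its natural reading applies this to exploratory outcomes too. No V2 HRV comparison is specified, and mixed models are only a possibility. This stands. It confines the point to V2 and V4 summaries and to any model that draws on V2.

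Second, the phrase about having V2 immediately comes from an estimate of the shortest time in the study, not from a visit procedure. The visit section speaks of participants returning, which suggests a separate trip. V2 also includes more than ten questionnaires in no stated order, so even a same-day recording might follow a long seated task. This stands as a reason for caution about frequency and timing. It does not remove the permission, because two other places open the window at 0 days.

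Third, several stronger readings are tempting, and the documents do not support them:
- *That many V2 visits fall on day 0.* The exploratory figures also fit none. They come from a study that averaged 8.6 sessions, and a visit on day 1 would count as early without being affected.
- *That the early arm has an hour of eyes-closed rest that controls never have.* Stated eyes-closed protocol time is 16-48 minutes, and controls who cross over have the same sessions before V4.
- *That HR/HRV are the only objective outcomes.* Counts of hospital, emergency, urgent care and clinic visits are also collected, although their source is not stated.
- *That same-day recordings should be discarded.* At V2 this would remove data from the early arm alone, according to scheduling after randomisation, and so create missingness that depends on arm.

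**Conclusion.** The gap is real and minor. The plan permits the early arm's V2 HR/HRV recording on the day of session 4, sets no minimum interval and gives controls no comparable rest. Acute post-session state and treatment effect can therefore be mixed in exploratory V2 comparisons and in mixed models that use V2. At V4 the issue is one of within-person change.

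A reader might infer that the trial's main result, or its HRV evidence as a whole, is compromised. It is not: PSS at V3 and HR/HRV at V3 are unaffected. The size is unknown, since both the share of same-day recordings and the acute shift would have to be assumed; the 0.05-0.30 SD range above is an illustration, not an estimate. The conclusion rests on the timing rules in the available text and on heart rate and HRV responding to recent rest. This is a cheap improvement of low priority.

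**What to change.** - In the Abstract, the Schedule of Activities, Number of CR Sessions and Length of Study, and Post-Intervention Data Collection Visits, schedule the V2 and V4 Faros recordings on a calendar day without a CR session, so that the recording window opens at day 1 after the last session.
- In the same edit, reconcile the 7-day and 0-14-day limits for the early arm's V2.
- Record the time from last session to each V2 and V4 recording.
- In the Analytical Plan, name V1 to V3 as the main HR/HRV contrast. Keep any same-day recordings in the main V2 and V4 summaries, and prespecify a sensitivity analysis without them.

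The cost is a short amendment to an assessment window and one extra time field. Some participants who could have combined V2 or V4 with their last session will need a separate trip, with a small risk of missed visits among working healthcare staff. Sessions and V3 do not change.

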Heart Rate (HR), and Heart Rate Variability (HRV):

Continuous heart rate will be recorded while the participant is breathing normally in seated position for 10 minutes using Faros 180 heart rate monitor (Bittium Corporation, Oulu, Finland). Beat to beat intervals (RRI) files will be generated at 1000 Hz via the data acquisition software. The files will be analyzed with Nevrokard HRV software (by Nevrokard Kiauta, d.o.o., Izola, Slovenia). The recordings will be visually inspected to ensure data quality (dropped beats or gross motion artifacts are excluded) and the first 5 minutes of usable tracings will be analyzed. Measures of heart rate variability (HRV) in the frequency domain will be derived and these measures will be integrated over specified frequency ranges (LF: 0.04-0.15 Hz; HF: 0.15-0.4 Hz). Power of RRI spectra in LF, HF range (LF_{RRI} and HF_{RRI}) and total power (TP) will be calculated in normalized units and the ratio of LF/HF will be used as a measure of sympathovagal balance. ("Heart rate variability: standards of measurement, physiological interpretation and clinical use. Task Force of the European Society of Cardiology and the North American Society of Pacing and Electrophysiology," 1996). Data are saved to Excel spreadsheets for further statistical analysis by study team members.

Exploration for Unexpected Barriers, Challenges, or Detrimental Factors:

A REDCap element will be added to data collection at V3 and V5, the final official data collection visit, seeking input regarding any challenges or barriers faced during the study related to factors such as availability of session dates or times, restrictive guidelines for when sessions need to occur, tasks performed during data collections, comfort of the session chair/equipment, difficulty sitting still, office location and accessibility trouble, competing other therapeutic modalities, length of the research study, or any other issues.

Analytical Plan:

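### With fixed LF and HF bands and free breathing, respiratory power below about 9 breaths/min is counted as LF, and the plan provides no breathing rate to show it (exploratory HRV only)

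*Combined protocol and SAP*

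**What the plan says.** The protocol section on heart rate and HRV sets the recording conditions: "Continuous heart rate will be recorded while the participant is breathing normally in seated position for 10 minutes". Breathing is therefore free, not paced. The signal kept is the beat-to-beat series: "Beat to beat intervals (RRI) files will be generated at 1000 Hz via the data acquisition software". Quality control concerns beats and movement only: "dropped beats or gross motion artifacts are excluded) and the first 5 minutes of usable tracings will be analyzed". The spectral measures are "integrated over specified frequency ranges (LF: 0.04-0.15 Hz; HF: 0.15-0.4 Hz", and "the ratio of LF/HF will be used as a measure of sympathovagal balance".

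The Schedule of Activities has one physiological row, "FAROS HRV Recording", marked at V1 to V5, and no row for respiration. The Analytical Plan names no respiratory covariate and no sensitivity analysis for HRV. The Abstract and Objectives class HRV as exploratory.

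The CR Sessions section says of the intervention: "All protocols will occur with eyes closed, and participants will be instructed to relax". That describes the sessions, not the HRV recordings.

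**The concern.** The reading of LF/HF as sympathovagal balance relies on vagal, breathing-linked oscillation falling in the HF band. That is general physiology and is not stated in the protocol, but the planned interpretation depends on it. The oscillation sits at the breathing frequency, and the band edge does not move with it. A participant who breathes slowly enough at one visit moves that power from HF to LF, and the ratio then points towards less vagal balance when nothing has changed, or when vagal modulation has risen.

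The intervention aims at relaxation, and the control arm has no sessions before V3. If relaxation left early-arm participants breathing more slowly at V2 or V3, the error would differ by arm. If it did not, recordings that cross the edge at only one visit would still add noise to the change scores. At stake is the interpretation of LF, HF and LF/HF, which the protocol wants for exploring autonomic effects and planning later trials. The primary result is not at stake.

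**Working it through.** The plan gives no figure to reproduce here, so the check runs from its band limits.

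**1. Band edges in breaths per minute** (Hz × 60; limits from the HRV section)

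- 0.04 × 60 = 2.4
- 0.15 × 60 = 9.0
- 0.40 × 60 = 24.0

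HF covers 9 to 24 breaths/min and LF covers 2.4 to 9.

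**2. Direction.** If a share s of HF power is counted as LF, the ratio becomes (LF + s·HF) / (HF·(1 − s)), which exceeds LF/HF for every s > 0.

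| LF, HF | s = 0 | s = 0.25 | s = 0.5 | s = 0.8 |
|---|---|---|---|---|
| 500, 500 | 1.0 | 1.67 | 3.0 | 9.0 |
| 800, 400 | 2.0 | 3.0 | 5.0 | 14.0 |

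**3. Size in one recording** (simulation; amplitudes and noise assumed). A 5-minute series with a 0.095 Hz LF rhythm of amplitude 25, a respiratory component at the breathing rate, noise SD 10 and a Welch spectrum gives these medians:

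| Breaths/min | LF/HF, respiratory amplitude 25 | LF/HF, respiratory amplitude 35 |
|---|---|---|
| 10 to 15 | 0.98 | 0.51 |
| 9.5 | 1.12 | 0.61 |
| 9 | 5.41 | 4.09 |
| 8.5 | 49.8 | 72.2 |

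Raising respiratory amplitude by 40% lowers LF/HF at 10/min or above, as intended, but below the edge the ratio rises. Leakage starts the distortion slightly above 9/min.

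Other assumed settings give other sizes:

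- 0.84–1.51 at 10/min against 11.4–15.8 at 8.5/min. On the log scale the shift is ln(11.4/1.51) = 2.0 to ln(15.8/0.84) = 2.9.
- With 20–30% breath-to-breath variation, 2.1–2.7 against 6.6–7.9, a shift of about 0.9 to 1.3.
- The table above gives ln(49.8/0.98) = 3.9.

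The direction is the same throughout; the size is not.

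**4. Between-arm bias** (all assumed: normal breathing rates, slowing in the early arm only, shift 2.6 log units per affected recording, SD of change 0.9, 69 per arm, which is half of the 138 target). SE = 0.9 × √(2/69) = 0.153. Bias = 2.6 × excess share of early-arm recordings below 9/min.

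| Mean, SD | Slowing | Share below 9/min, before → after | Excess | Bias | Bias/SE |
|---|---|---|---|---|---|
| 15, 2 | 1 | 0.13% → 0.62% | 0.49% | 0.013 | 0.08 |
| 15, 3 | 0.5 | 2.28% → 3.34% | 1.06% | 0.028 | 0.18 |
| 16, 3 | 1 | 0.98% → 2.28% | 1.29% | 0.034 | 0.22 |
| 15, 3 | 1 | 2.28% → 4.78% | 2.50% | 0.065 | 0.42 |
| 14, 3 | 2 | 4.78% → 15.87% | 11.09% | 0.288 | 1.88 |

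The last row holds the SD at 0.9. If independent crossings add their own variance, 2.6² × p(1 − p) per recording, the SE becomes 0.223 and the ratio falls to 0.288/0.223 = 1.3. The bias scales with the shift. At 3.9 the last row gives 0.44, which is 2.8 SE with the SD held at 0.9 but 1.5 SE once the crossing variance is included. At 0.9 it gives 0.10, or 0.65 SE. These are illustrations, not bounds.

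**The case against.** The strongest objection is that no arm difference is documented. The instruction to relax applies during sessions. The HRV recordings are made at separate visits, and V3 falls 4–7 weeks after V2. Nothing in the protocol says that breathing slows or stays slow. Without an arm difference there is noise but no between-arm bias, and anyone breathing at 10/min or above is essentially unaffected. This stands, so the arm effect can only be stated conditionally.

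A reader might infer several stronger things that the documents do not support:

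- **That the damage could not be detected later.** The beat-to-beat files are kept, and breathing rate can be derived from them. The gap is that nothing in the plan asks anyone to do so.
- **That HRV is the only objective outcome.** Heart rate is listed alongside it, and the band split does not affect it.
- **That breathing rate is certainly not recorded.** The coordinator's data collection forms (Appendix E) and part of the safety text were not available. What can be said is that no available text plans it.

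The protocol cites a published measurement standard for its HRV methods. That supports the choice of bands, but it does not alter the arithmetic at the 0.15 Hz edge.

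An obvious remedy, an HF band centred on each person's breathing frequency, can reverse the error. At 8.5/min (0.142 Hz) a ±0.05 Hz band runs from 0.092 to 0.192 Hz and takes in an LF rhythm near 0.1 Hz. In simulation LF/HF then falls to about 0.04–0.19 at 8.5/min and close to zero at 6–7/min, which would look like vagal benefit. This stands too and limits what the fix should rely on.

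**Conclusion.** The point holds as a cheap improvement confined to the exploratory HRV outcomes. The 9 breaths/min threshold and the direction of the error follow from the plan's own band limits, given that respiratory-frequency power is vagal. The number of affected recordings is unknown because the documents give no breathing rates. At an assumed shift of 2.6 log units, the between-arm bias in ln(LF/HF) runs from under 0.1 to about 1.9 SE. The breathing rates, the slowing, the SD of change and the log scale are also assumptions.

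It would be tempting to conclude that the plan will hide a real autonomic benefit or report it as a sympathetic shift in the early arm. That requires slower breathing in that arm at the recording visits, which is possible but not shown. Moving power across 0.15 Hz changes neither total power nor mean heart rate, and the PSS, ISI and GAD-7 analyses are unaffected.

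**What to change.** In the HRV section:

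1. State that breathing rate will be derived from the existing beat-to-beat recording, or noted as a one-minute count during it. Report it, with the share of recordings below 9/min, by arm and visit.
2. Keep the fixed-band analysis with all participants.
3. State in advance that LF, HF and LF/HF from recordings with a respiratory peak below 0.15 Hz will not be interpreted as sympathovagal balance. For those recordings rely on heart rate and total power. Total power should be kept in absolute units for this use, because the section refers to normalized units.
4. Show one sensitivity result with those recordings flagged or with breathing rate taken into account.
5. If a breathing-centred HF band is also shown, fix its width beforehand and note that near 6–8 breaths/min it overlaps the 0.1 Hz rhythm and can bias LF/HF downward.

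The cost is one derived variable and one more exploratory result, with no extra visits or participants. The sensitivity result conditions on breathing rate, which treatment may itself change, so it should be labelled supportive only.
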